3 RSA DESIGN

This study is a multi-center, randomized, placebo-controlled trial, testing active dose of pridopidine (45mg BID), given orally daily versus placebo. Participants will be randomized 3:1 active: placebo.

The study will consist of a screening/baseline visit, a 2-week double-blind, placebo-controlled up-titration period, a 22-week double-blind, full-dose, placebo-controlled treatment period, and a 28-day safety follow-up period (after the last dose of IP) for those participants who do not enter the Open Label Extension (OLE) period of the study.

After signing informed consent, participants will undergo screening assessments to determine eligibility and eligible participants will be randomly assigned in a 3:1 ratio to 1 of 2 study intervention groups:

- Treatment Arm 1 (active): pridopidine 45 mg orally (PO), BID (total daily dose of 90 mg after two week up-titration period at 45mg PO, QD)
- Treatment Arm 2 (control): matching placebo, PO BID

During the 2 week up-titration period (starting on Day 1), all participants will self-administer 1 capsule of study intervention PO once daily (QD) in the morning. In the full-dose treatment period (starting on Day 14) study intervention will be taken BID, in the morning and in the afternoon (approximately 7-10 hours apart). Participants who complete all scheduled visits will have the option of participating in the OLE period of the study.

Throughout the study, participants will be assessed through on-site clinic visits and telephone calls, as specified in the Schedule of Activities (SoA) table.

For participants who complete all scheduled visits, their final visit will be the Follow-Up Safety Call (28 days after the Week 24 clinic visit), unless participants continue on in the OLE. Participants who discontinue study intervention early will be encouraged to complete all other visits as scheduled for the full course of the study per ITT. For participants who withdraw early from the placebo-controlled period, an in-person Early Termination Visit and a Follow-up Safety Call should be conducted. At the Early Termination Visit the same procedures as described for the Week 24 visit should be conducted. At the Follow-up Safety Call, information on clinical status should be collected.

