3.2 End of Participation Definition

HEALEY ALS Platform Trial
Regimen-Specific Appendix D, Pridopidine
Version 2.0, 15-July-2021
CONFIDENTIAL

A participant is considered to have ended his or her participation in the placebo-controlled period of the Regimen if they:

- Complete planned placebo-controlled period visits, as described in the SOA, including participants on or off study drug
- Early terminate from the study and complete the Early Termination Visit and Follow-Up Phone call as described in Section 6.1.11
- Withdraw consent to continue participation in the study or are lost to follow-up

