4.4 ECG Monitoring

In addition to the ECG performed at the Master Protocol Screening visit, additional ECG monitoring with stopping and monitoring rules will be completed as described below:

QT Stopping Rules:

- QTcF > 500 ms or
- QTcF > 480 ms AND Δ QTcF > 60 ms from regimen baseline value (pre-dose)
 - The regimen baseline QTcF value is the average of triplicate ECGs collected **pre-dose** during the regimen Screening Visit.
 - For all subsequent visits the Δ QTcF is calculated using the regimen baseline QTcF value (pre-dose), as described above (average triplicate screening QTcF).
 - For Baseline post dose visit only, Δ QTcF is calculated from the initial printout, as the ERT Overread will not be available at the time of the Baseline Visit.
 - For all other ECGs (i.e. Week 4 and Week 24), Δ QTcF should be calculated using the baseline QTcF pre-dose (average triplicate screening QTcF) **from the ERT Overread**.
 - For participants who transition into the OLE, the new baseline QTcF is the average triplicate QTcF collected **pre-dose** during the Week 24 visit.
- If a participant meets either of the above stopping rules, IP must be held and the participant will be asked to return to the clinic after 3-14 days for a follow up ECG.
- If the local ECG reading results at the site match either of the above stopping rules, the IP will be held until the ERT overread report is received. If the ERT overread does not confirm a participant meets the stopping rule above, then the participant can restart the study drug.
- If a participant meets either of the above stopping rules, confirmed by the ERT overread, IP must be discontinued and the participant will be asked to return to the clinic after 3-14 days for a follow up ECG.

QT Monitoring Rule:

- QTcF > 480 ms OR Δ QTcF > 60 ms from regimen baseline value (pre-dose)
 - The regimen baseline QTcF value is the average of triplicate ECGs collected **pre-dose** during the regimen Screening Visit.
 - For all subsequent visits the Δ QTcF is calculated using the regimen baseline QTcF value (pre-dose), as described above (average triplicate screening QTcF).
 - For Baseline post dose visit only, Δ QTcF is calculated from the initial printout, as the ERT Overread will not be available at the time of the Baseline Visit.

Figure 2: ECG Monitoring Flow for Regimen Specific Screening Visit to Assess for Regimen D Eligibility* (before IP administration):

Initial ECG assessment will be done to assess eligibility (Figure 2):

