5.8 Participant Compliance

Responsible study personnel will dispense the study drug. Participants will be requested to return any unused IP including empty packaging and used bottles at each study visit. Treatment compliance will be assessed at in clinic study visits through bottle counts and will be

documented and summarized by a drug-dispensing log for each participant. During phone visits, drug compliance check-in will be held to ensure participant is taking drug per dose regimen and to note any report of missed doses. Participants will be counseled on the importance of taking the IP as directed at all study visits. If poor compliance continues, (i.e., multiple missed doses resulting in less than 80% overall compliance), discontinuation of the participant from the trial should be considered and discussed with the Medical Monitor.

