6.1.10 Process for Early Terminations

A research participant may choose to discontinue their participation at any time for any reason. The SI or designee will encourage the participant to follow the study protocol under intent-to-treat principle and follow the study visits, off treatment, up to the week 24 visit. If a participant decides to discontinue IP, but will complete the protocol, an in-person Early Termination Visit and Follow-Up Safety Call is not necessary.

Participants who early terminate from the study and do not complete the protocol will be asked to be seen for an in-person Early Termination Visit and complete a Follow-Up Safety Call. If a participant is not able to be seen in-person, safety assessments and others that can be conducted remotely should be performed.

The in-person Early Termination Visit should be scheduled as soon as possible after a participant early terminates. If the participant early terminates during the placebo-controlled portion of the Regimen, all assessments that are collected at the Week 24 in-clinic visit should be conducted. If the participant early terminates during the OLE period, all assessments that are intended for collection at the OLE Week 24 in-clinic visit should be conducted. The Follow-Up Safety Call should be completed approximately 28 days after the last dose of IP.

If the Early Termination Visit occurs approximately 28 ± 3 days after the last dose of IP, the information for the Follow-Up Safety Call can be collected during the Early Termination Visit, and a separate Follow-Up Safety Call does not need to be completed. If the in-person Early Termination Visit does not occur within 28 ± 3 days of the last dose of IP, the Follow-Up Safety Call should occur approximately 28 ± 3 days after the last dose of IP and the Early Termination Visit will be completed after the Follow-Up Safety Call.

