6.1 Analysis Sets

The ITT analysis set is henceforth referred to as the Full Analysis Set (FAS) and defined as follows:

- Full Analysis Set (FAS): Participants who were randomized within RGD plus placebo participants from specified regimens, classified according to their randomized treatment assignment. Participants who discontinue study drug but remain in the study will be included in the FAS. Observations completed after regimen data lock are excluded. Participants determined to not meet ALS diagnostic criteria are excluded.

The definition of the STF analysis set is revised as follows:

- Safety Full (STF) Set: Participants who initiated treatment within RGD plus placebo participants from specified regimens who are not known to be ineligible for RGD and who initiated treatment in their respective regimen, classified according to the treatment they actually received. Observations made after premature permanent discontinuation of study drug are included in this sample, should such participants remain on study. Observations completed after regimen data lock are excluded.

An analysis set restricting shared placebo participants to those regimens in which study drug is administered by the same route as RGD is defined as follows:

- Efficacy Common Mode of Administration (ECM) Set: The subset of participants in the FAS analysis set who are in regimens in which study drug is administered by the same route as RGD.

The definitions of the ECC, ERO, STN, and SRO analysis sets are the same as described in the M-SAP with reference to the ITT analysis set now referencing the FAS analysis set. The following analysis sets are specific to RGD:

- Modified Intention-to-treat (mITT) Set: Participants who were randomized within RGD plus placebo participants from specified regimens, who received at least one dose of study drug, and who completed at least one post-baseline ALSFRS-R assessment, classified according to their randomized treatment assignment. Participants who discontinue study drug but remain in the study will be included in the mITT. Observations completed after regimen data lock are excluded.

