- Efficacy Per-protocol (EPP) Set: The subset of participants in the FAS analysis set who initiated study treatment and who were not involved in protocol deviations related to eligibility, treatment, follow-up, or assessment, classified according to the treatment they actually received. Final specification of participants included vs. excluded from the EPP analysis set will be defined prior to data lock. Inclusion or exclusion from the EPP analysis set of any participant for whom treatment assignment was unblinded prior to data lock will be governed by the prespecified criteria above. If a participant's data is truncated for inclusion in the EPP analysis set due to a time-dependent event, e.g., initiation of a prohibited medication or non-adherence to protocol-specified dosing, clinical events observed up to 28 days after the censoring event will be included in the EPP analysis set. Data from placebo participants shared from other regimens will not be truncated due to non-adherence to protocol-specified dosing.

Applicable analysis sets (FAS, mITT, ECM, EPP, STF, and STN) will include shared placebo participants from regimens A, B, and C. As only concurrently enrolling regimens are contributing to efficacy analyses, the FAS and ECC analysis sets are synonymous in RGD and only the FAS analysis set will be referenced. As regimen A is administered by subcutaneous injection and regimens B and C are administered orally, only regimens B and C will contribute shared placebo participants to the ECM and STN analysis sets.

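### Protocol Section 5.8 names leaving the trial, rather than stopping study drug, as the step to consider for continued compliance below 80%, which sits awkwardly with off-drug follow-up and the treatment-policy estimand

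*Protocol*

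**What the plan says.** Protocol Section 5.8 checks compliance by bottle counts at clinic visits and by a check-in at phone visits, and has participants counselled at all visits. If poor compliance continues, described as multiple missed doses that bring overall compliance under 80%, "discontinuation of the participant from the trial should be considered and discussed with the Medical Monitor". The section does not mention stopping drug while keeping follow-up.

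Other parts of the protocol treat stopping drug and leaving the study as separate matters:

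- Section 3, citing ITT: "Participants who discontinue study intervention early will be encouraged to complete all other visits as scheduled".
- Section 3.2 recognises as one way of ending participation that participants "Complete planned placebo-controlled period visits, as described in the SOA, including participants on or off study drug".
- Section 4.4, for a QT stopping rule that is met and "confirmed by the ERT overread, IP must be discontinued and the participant will be asked to return to the clinic". This ends the drug, not participation.
- Section 6.1.10 has sites encourage participants to "follow the study visits, off treatment, up to the week 24 visit". For those who do terminate early in the placebo-controlled period, "all assessments that are collected at the Week 24 in-clinic visit should be conducted".

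The SAP follows the same separation. Section 6.1 states: "Participants who discontinue study drug but remain in the study will be included in the FAS". Sections 6.3 (primary model) and 6.5.3 (random-slopes model, primary for SVC) use a treatment-policy strategy for discontinuation. Data collected after discontinuation are used; missing data are not imputed and are assumed missing at random.

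**The concern.** The only action Section 5.8 names is the one that loses outcome data. The analysis does not need it. The full analysis set keeps non-compliers, and the per-protocol set can already truncate data for time-dependent events such as "initiation of a prohibited medication or non-adherence to protocol-specified dosing". A participant with a confirmed QT stopping event stays in follow-up, while one who misses capsules may be taken out of the trial.

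If a site acts on the clause, the estimand still asks for the later ALSFRS-R and SVC values, but they do not exist and the models assume they are missing at random. Poor compliance arises after randomization and may be related to tolerability or progression. One inferred route is worsening swallowing, since capsules are swallowed whole unless a gastrostomy tube is used (Section 5.5). The missing-at-random assumption would then be less comfortable than for administrative losses.

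**Working it through.** The documents state no compliance rate, removal rate or power figure, so there is no plan figure on this point to reproduce. The check covers assessments lost per person, scale under assumed rates, how hard the trigger is to reach, and which endpoints are exposed.

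**Loss per removed participant.** SAP Section 2.9 schedules post-baseline ALSFRS-R at Weeks 4, 8, 12, 16, 20 and 24 (6) and SVC at Weeks 8, 16 and 24 (3). Net loss = scheduled assessments after removal − 1 for the Early Termination Visit, assuming that visit is held.

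| Removal | ALSFRS-R | SVC |
|---|---|---|
| After Week 8 | 4 − 1 = 3 of 6 | 2 − 1 = 1 of 3 |
| After Week 16 | 2 − 1 = 1 of 6 | 1 − 1 = 0 of 3 |

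In the last cell, the final SVC is taken earlier rather than lost.

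**Scale (removal rate assumed).** With 160 planned participants, 160 × 6 = 960 ALSFRS-R and 160 × 3 = 480 SVC assessments are scheduled.

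- 5% removed (8 people), after Week 8: 8 × 3 = 24; 24/960 = 2.5% of ALSFRS-R. SVC: 8/480 = 1.7%.
- 5% removed, after Week 16: 8/960 = 0.8% of ALSFRS-R. SVC: 0.
- Range of 1% to 10% (1.6 to 16 people): ALSFRS-R 0.5% to 5.0% after Week 8, and 0.17% to 1.7% after Week 16.
- If regimens A to C add 120 shared placebo participants (assumed, 40 each) with no such loss, the denominator is 280 × 6 = 1,680. At 5%, the loss is 24/1,680 = 1.4% or 8/1,680 = 0.5%.

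As an outer bound, suppose removed participants lost all their data and take SE ∝ √(1/n_active + 1/n_placebo). At 5% removal, the SE rises by a factor of √[(1/114 + 1/38)/(1/120 + 1/40)] = 1.026 with regimen controls only. With the assumed sharing it is √[(1/114 + 1/158)/(1/120 + 1/160)] = 1.018. The real loss would be smaller, because earlier visits are kept. This is a simple two-group comparison, not the Bayesian model.

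**The trigger.** Assuming visits on target days and BID dosing from Day 14:

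- By Week 8: 14 + 42 × 2 = 98 capsules. 80% is 78.4, so at least 20 must be missed.
- By Week 16: 14 + 98 × 2 = 210 capsules. 80% is 168, so at least 43 must be missed.

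**Which endpoints are exposed.**

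- Primary model (ALSFRS-R) and SVC slope: later values are missing and assumed missing at random. The hierarchical SVC endpoint covers only participants with bulbar dysfunction at baseline.
- Time-to-event secondaries 1 and 4 (SAP Section 6.5.1): a decline already recorded counts. Under Section 3.6, early termination due to disease progression also counts as the event. Otherwise the primary analysis makes no imputation, and no event is counted.
- Bulbar responder endpoint: recorded worsening, or early termination due to disease progression, makes a participant a non-responder. Only the remainder are imputed under missing at random, from the same arm.
- Survival: SAP Section 5.10 does not censor at consent withdrawal, and vital status is sought for every randomized participant (Protocol Schedule of Activities, footnote 12).

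**The case against.** The strongest reply is that no rule is broken. Section 5.8 applies only when poor compliance continues, counselling is already in place, and removal is something to consider with the Medical Monitor. Section 3.2 recognises early termination as an end of participation. Section 6.1.10 begins with participants who choose to stop and only encourages off-drug visits. The two texts can coexist. That stands: this is a tension, not a contradiction.

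The loss figures compare removal with full attendance to Week 24. Some persistent non-compliers would miss visits or withdraw anyway. That also stands, so the counts are ceilings at each assumed rate.

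The SAP already covers part of the informative case. Progression-related termination is not left to missing at random for the event and responder endpoints. Multiple-imputation sensitivity analyses are planned (SAP Sections 3.6 and 6.5.10). These limit the damage but cannot recover assessments that were never made. A termination recorded as poor compliance would not, on that reason alone, fall under the progression rule.

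The Master Protocol and the Manual of Procedures are not among the documents and may say more about follow-up. SAP Section 1 ranks this appendix above the Master Protocol on non-analysis matters, so in a conflict Section 5.8 would govern. A clause that merely supplemented it could still help.

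**Conclusion.** The point holds as a minor one. Section 5.8 names the wrong action for a trial that wants data after drug discontinuation. Acting on it would cost up to a net 3 of 6 ALSFRS-R and 1 of 3 SVC assessments per person after Week 8, or 1 of 6 and 0 of 3 after Week 16, given an Early Termination Visit.

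A reader might infer more, and the documents do not support it:

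- That non-compliers must be removed. The clause leaves this to judgement.
- That the primary result is biased or materially underpowered. The number affected is unknown and may be zero, and the effect on bias or precision in the primary model cannot be derived from these documents.
- That all secondaries are compromised. The gap in the event and responder endpoints is limited to participants with no recorded decline whose termination is not recorded as due to progression, and survival is largely protected.

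The 5% rate, its 1% to 10% range and the 120 shared placebo participants are assumptions used for scale only.

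**What to change.** In Section 5.8, replace the reference to discontinuing the participant from the trial with *discontinuation of study drug may be considered*, keeping the discussion with the Medical Monitor. Then add: *Poor compliance alone should not end study participation; whether or not study drug is stopped, participants will be encouraged to complete scheduled assessments to Week 24, consistent with Section 6.1.10.*

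The word *encouraged* matches the strength of Section 6.1.10. A partial complier may stay on drug if the site and the Medical Monitor agree, and participants may still withdraw at any time.

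The cost is one changed phrase and one added sentence, with no visits beyond those already scheduled. It is cheap rather than free: sites and the Medical Monitor give up the option to end participation for poor compliance alone. The sponsor could reasonably make this change, but the trial does not depend on it.

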5.9 Overdose

Certain safety events that occur in association with IP may require reporting. These safety events include, but are not limited to, the following:

- Overdose of the IP, where ‘overdose’ is defined as a participant ingesting more than 3 times the intended dose
- Suspected abuse/misuse of the IP
- Inadvertent or accidental exposure to the IP
- Medication error involving IP (with or without participant exposure to the IP, e.g., name confusion)

These safety events should be reported to the Coordination Center whether they result in an AE/SAE or not. Safety events associated with an AE/SAE should also be reported in the EDC. In the event of overdose, study staff should monitor the participant and provide supportive care as needed. The SI should also contact the Medical Monitor within 24 hours of the SI’s awareness.

5.10 Prohibited Medications

Excluded Medications:

Class	Drugs
Antipsychotics	Clozapine, haloperidol, mesoridazine, thioridazine, pimozide, chlorpromazine, perphenazine, risperidone, zuclopenthixol, and sulpiride.
Antiarrhythmic	Disopyramide, procainamide, flecainide, propafenone, amiodarone, dofetilide, ibutilide, and sotalol
Others	Astemizole, terfenadine, azithromycin, erythromycin, moxifloxacin, pentamidine, sparfloxacin, clarithromycin, chloroquine, halofantrine, bepridil, cisapride, domperidone, droperidol, levomethadyl, sevoflurane, anagrelide, budipine, fluconazole, levofloxacin, lidoflazine, ondansetron, probucol, terodiline, vandetanib, tramadol, tamoxifen, atomoxetine, tolterodine

Participants who use the above medications while enrolled in Regimen D of the HEALEY ALS Platform Trial increase their risk of QT prolongation and torsades. If participants inadvertently use these medications while they are on IP, the Medical Monitor should be notified and a single 12-lead ECG should be collected within 3-14 days of initiating the new prohibited co-medication, or higher dose, to test for QTcF prolongation meeting the Monitoring or Stopping Rules.

If there is a clinical indication for any medication specifically prohibited during the study, the Medical Monitor will be notified and engaged in consultation as to how to address.

5.11 Pridopidine Known Potential Risks and Benefits

5.11.1 Known Potential Risks

QT prolongation:

In the PRIDE-HD trial of 408 participants, the cardiac effects of pridopidine were evaluated in people with HD at doses up to 112.5 mg BID for 52 weeks. Although low, there was a higher overall incidence of AE-reports of QT prolongation in pridopidine-treated participants compared to placebo-treated participants: 1.5% in pridopidine-treated participants vs 0% in placebo-treated participants. However, there was no evidence of a dose response in QT-related AEs (QT prolongation AEs: 0 in placebo, 2 in 45 mg BID, 0 in 67.5 mg BID, 1 in 90 mg BID and 2 in 112.5 mg BID; total 5/327=1.5%). Using the PRIDE-HD data, a cardiac exposure-response model was developed utilizing ECG data paired with PK samples collected for up to a year. Only ECGs that were paired with PK samples (n=3071) were used to develop the cardiac exposure-response model, which was based on 2753 ECGs from pridopidine-treated participants and 763 from placebo-treated participants.

A concentration-dependent effect of pridopidine on the QTcF interval was observed in this study, with a slope of 0.012 ms per ng/mL (90% CI: 0.0109 to 0.0127 ms per ng/mL).

At 45 mg BID, the predicted QT effect ($\Delta\Delta\text{QTcF}$) in participants with HD was 6.6 ms (with an upper bound of the 90% CI 8 ms), which is not clinically meaningful. Pridopidine 45 mg BID is the dose to be tested in the HEALEY ALS Platform Trial. Although this was not a clinically meaningful QT effect, as there is no prior experience with pridopidine in the ALS patient population, we plan to include additional safety monitoring and risk mitigation measures.

